3. STUDY DESIGN

3.1 DESCRIPTION OF THE STUDY

This will be a placebo controlled, double-blind, randomized, Phase II dose escalation trial completed at up to 6 study centers. Subjects will be randomized in a 2:1 ratio to treatment or control in blocks of 15, performed twice per dose - low (0.25 mg/kg with maximum dose 25 mg) and high (0.50 mg/kg with maximum dose 40 mg), with randomization stratified by site.

3.2 END OF STUDY AND LENGTH OF STUDY

The anticipated first patient, first visit will occur on June 15, 2020. Enrollment is anticipated to take approximately 5 months, with our last patient, first visit to occur on November 15, 2020. Follow up will be completed by December 15, 2020. It will take the study team approximately 2 Tenecteplase-Icahn School of Medicine at Mount Sinai Protocol ML42492

months to clean and analyze the data, with a final study report expected by mid-February, 2021.

The total length of the study, from screening of the first patient to the end of the study, is expected to be approximately 8 months.

3.3 RATIONALE FOR STUDY DESIGN

This is a phase II dose escalation study intended to evaluate the potential safety and efficacy of tenecteplase for the treatment of COVID-19 associated respiratory failure. This study is not powered for significance, but is instead designed to provide an estimate of the potential benefit-signal and better inform a subsequent phase III RCT.

3.3.1 Rationale for Tenecteplase Dose and Schedule

Tenecteplase is a triple combination mutant of alteplase, with a longer half-life, improved specificity for fibrin, and higher resistance to degradation by plasminogen-activator inhibitor.²² One practical clinical advantage over other thrombolytic drugs is the ability to bolus a single dose of tenecteplase, compared to longer infusions required for efficacy (i.e. alteplase). Tenecteplase was first studied in acute myocardial infarction (AMI) in the 1990s. In the TIMI 10A trial, tenecteplase was found to be effective for coronary reperfusion in patients with AMI and had a safety profile comparable to wild-type tPA.²³ The follow up TIMI 10B trial randomized 886 patients with early (≤ 12 hr) AMI to either bolus tenecteplase or bolus + infusion of tPA, plus coronary angiography and postprocedural heparin infusion.²⁴ The study authors found that overall rates of TIMI grade 3 reperfusion were similar between the two groups, but this finding was found in patients who received higher doses of tenecteplase (50 mg versus 30 mg), albeit with higher risk of symptomatic bleeding and intracranial hemorrhage. The risks of hemorrhage were reduced in both groups by lowering heparin infusion rates. A further safety assessment of tenecteplase, relative to alteplase, was published in 1999 through the ASSENT-1 trial, in which a total of 325 patients were given a single bolus of tenecteplase in escalating doses (30, 40, or 50 mg).²⁵ Overall rates of intracranial hemorrhage were low (0.77% overall), did not depend on dose, and were comparable to historical data on tPA. Overall, the authors recommend a weight-based dosing strategy for patients with AMI.

Based on these positive safety trials, subsequent trials were published directly comparing tenecteplase and alteplase. ASSENT-2 was a double-blind, controlled trial randomizing 16,949 patients to either weight based tenecteplase bolus (0.5 mg/kg) or infusion with tPA, plus aspirin and heparin infusion.²⁶ The primary outcome of all-cause mortality at 30 days was similar for the two groups (6.18% and 6.15% for tenecteplase and tPA, respectively). Rates of intracranial hemorrhage were also similar between the two groups, although the risk of other hemorrhage was higher for tPA.

Given the positive results in the cardiac literature, tenecteplase has also been trialed for acute ischemic stroke; however, there has been limited adoption compared to alteplase following the NINDS trial in 1995.²⁷ Smaller phase II trials were performed throughout the 2010s, again suggesting equivalent efficacy regarding reperfusion with a similar safety profile between tenecteplase and alteplase. The first dose-escalation study was published in 2005 and assessed tenecteplase doses between 0.1 and 0.5 mg/kg.²⁸ Despite an increasing incidence of asymptomatic intracranial hemorrhage (ICH) between 0.1 and 0.4 mg/kg doses, no symptomatic ICH were seen. However, the 0.5 mg/kg tier was terminated prematurely given a high incidence

of symptomatic ICH (2 of 13 patients). Overall long-term functional outcomes were similar between the lower dose tenecteplase and historical controls treated with tPA.

The ATTEST trial randomized 104 patients with acute ischemic stroke to receive either TNK or tPA.²⁹ The primary endpoint of salvaged penumbra was identical between the two groups (68%), and rates of symptomatic intracranial hemorrhage were not statistically different (2% and 4% for TNK and tPA, respectively, $p=0.55$). Another randomized controlled trial published in 2012 assessed either alteplase infusion or dose-escalated tenecteplase (0.1 or 0.25 mg/kg) in patients with acute ischemic stroke less than 6 hours after symptom onset.³⁰ Patients treated with tenecteplase had better rates of radiographic reperfusion as well as short- and long-term clinical improvement, with higher doses (0.25 mg/kg) performing better than lower. Rates of intracranial and non-intracranial hemorrhages were consistent in all three groups.

Most recently the EXTEND-IA TNK trial assessed 202 patients randomized to either tenecteplase bolus (0.25 mg/kg) or alteplase prior to endovascular thrombectomy for large vessel occlusion.³¹ The primary outcome of angiographic reperfusion prior to thrombectomy (or absence of retrievable thrombus) was significantly greater in the TNK group, compared with tPA, present in 22% and 10%, respectively. Tenecteplase was also associated with improvement in 90-day functional outcomes, and similar rates of symptomatic intracranial hemorrhage.

Tenecteplase has also been assessed for use in treating pulmonary embolism (PE). In general, thrombolysis for PE has been shown to have minimal evidence for clinical benefit compared with heparin, except in those with the highest risks of recurrence or death.³² In clinical trials, thrombolysis with alteplase has been associated with improvements in hemodynamic parameters (including pulmonary resistance and cardiac index) but have indeterminate effects on overall clinical outcomes given a paucity of data.³³ In one randomized, placebo-controlled trial of tenecteplase (at a dose of 0.5 mg/kg) plus heparin versus heparin alone, intermediate-risk patients with PE treated with TNK had lower risk of hemodynamic decompensation or death.³⁴ Symptomatic intracranial hemorrhage was more frequent in the TNK group, though occurred predominantly in patients older than 75 years old. Patients with submassive PE have also been found to have increased odds of good outcome after treatment with tenecteplase, compared with placebo, according to a randomized trial published in 2014.³⁵

Based on this evidence, dosing guidelines for this trial will be as follows:

Patients will be monitored in the ICU immediately post-treatment and until 24 hours have passed and they are considered stable to downgrade to lower level of care.

- A. For patients already on therapeutic heparin, continue heparin infusion
- B. For patients not already on heparin or other anticoagulant, begin heparin with tenecteplase infusion starting with bolus dose of 60 Units/kg IV once (maximum dose of 5000 Units), followed by 12 Units/kg/hr (patients will only receive one dose of tenecteplase in total)
- C. For patients who were receiving enoxaparin at time of inclusion, tenecteplase infusion can be given immediately. Delay heparin to 12 hours after the most recent enoxaparin dose, beginning at an infusion rate of 12 Units/kg/hr. Do not administer a bolus dose of heparin.

-Check PTT every 6 hours; adjust heparin to achieve target PTT between 2 and 2.5 times ULN

Tenecteplase–Icahn School of Medicine at Mount Sinai
Protocol ML42492

12

Patients will continue with the unfractionated heparin infusion for 24 hours from the beginning of the study. After 24 hours, they may be transitioned to low molecular weight heparin according to institutional standard of care.

3.3.2 Rationale for Patient Population

This patient population has been chosen because they have objective indications of respiratory failure (intubation, NRB, HFNC, or NIPPV) but that failure is recent in onset. There has been increasing literature demonstrating the progressive thrombosis that occurs in multiple organ systems during COVID-19, including the lungs. By administering tenecteplase to this early stage respiratory failure population, who also have demonstrable thrombosis occurring (as indicated by their D-dimer) we hope to reverse the progressive pulmonary thrombosis that is occurring and thereby improve their outcome.

4. MATERIALS AND METHODS

4.1 PATIENTS

Approximately 60 total patients with COVID-19 will be enrolled in this study. 40 intervention (20 low dose subjects at 0.25 mg/kg with maximum dose 25 mg, 20 high dose subjects at 0.50 mg/kg with maximum dose 40 mg), 20 control subjects.

4.1.1 Inclusion Criteria

Patients must meet the following criteria for study entry:

- Patient/legally authorized representative has completed the Informed Consent Form
- Age ≥ 18 years
- Ability to comply with the study protocol, in the investigator's judgment
- Respiratory failure secondary to COVID-19 requiring mechanical ventilation for no greater than 48 hours, or high-flow nasal cannula (HFNC), non-rebreather (NRB) mask or non-invasive positive pressure ventilation (NIPPV) for less than 96 hours
- Confirmed infection with SARS-CoV-2 virus (PCR positive within 14 days)
- Elevated D-dimer (>2 times upper limit of normal within past 72 hours)
- For patient who are intubated >12 hours prior to randomization or with any evidence of neurologic deficit a head CT within 12 hours demonstrating no evidence of acute or subacute infarct or hemorrhage

4.1.2 Exclusion Criteria

Patients who meet any of the following criteria will be excluded from study entry:

General

- Current participation in another investigational drug study within the prior 7 days
- Known hypersensitivity or allergy to any ingredients of tenecteplase
- Active internal bleeding
- Known bleeding diathesis

Tenecteplase-Icahn School of Medicine at Mount Sinai
Protocol ML42492

- Use of one of the new oral anticoagulants within the last 24 hours (dabigatran, rivaroxaban, apixaban, edoxaban)
- Treatment with a thrombolytic within the last 3 months prior to randomization (exception for the use of Cathflo alteplase for occlusions of central venous catheters)
- Baseline platelet count <80,000/µL (results must be available prior to treatment)
- Baseline blood glucose >400 mg/dL (22.20 mmol/L)
- Baseline blood glucose <50 mg/dL needs to be normalized prior to randomization
- Intracranial or intraspinal surgery or trauma within 2 months
- Other, non-COVID-19 related, serious, advanced, or terminal illness (investigator judgment) or life expectancy is less than 6 months
- History of acute ischemic stroke in the last 90 days
- History of intracranial bleeding, including hemorrhagic stroke
- Presumed septic embolus; suspicion of bacterial endocarditis
- Mechanical ventilation > 48 hours, HFNC, NIPPV, NRB, or any combination, for greater than 96 hours
- Mechanical ventilation, HFNC, NRB, or NIPVV (for reasons other than obstructive sleep apnea) within the prior 30 days (excluding 96 hours prior to randomization)
- Moribund status suggesting imminent vascular collapse and inability to survive > 72 hours (investigator determination)
- Uncontrolled hypertension defined as systolic BP > 180 mm Hg and/or diastolic BP > 110 mm Hg
- Age > 75 years
- History of traumatic brain injury within 2 months
- Recent head trauma with fracture or brain injury
- History of Heparin Induced Thrombocytopenia (HIT) and/or other hereditary or acquired hemorrhagic diathesis or coagulation factor deficiency
- INR > 2 or recent oral anticoagulant therapy with INR >1.7
- Pregnancy or lactation within the prior 30 days; women of childbearing age (<55 years old) should have documentation of a negative pregnancy test
- Chronic liver disease defined as > Childs-Pugh Class B
- Patients with history of atrial fibrillation, mitral stenosis, or known left heart thrombosis
- Atrial fibrillation, mitral stenosis, or known left heart thrombosis
- Any other condition that, in the opinion of the investigator, precludes administration of tenecteplase or poses a significant hazard to the patient receives tenecteplase

4.2 METHOD OF TREATMENT ASSIGNMENT

This trial will be a randomized, blinded, placebo-controlled trial with an escalating-dose randomized design. Randomization will be completed as follows:

- Block randomization of 2:1 (treatment:control) in blocks of 15, performed twice per dose
- The first block of 15 patients (10 treatment at 0.25 mg/kg dose and 5 placebo control) will be assessed for safety trigger by the DSMC/CEC within 5 working days of the 15th patient completing 72 hours post treatment; if no safety trigger is met (as determined by DSMC/CEC), a second cohort of 15 patients will be enrolled (10 at the 0.25 mg/kg dose and 5 placebo control).
- If no safety trigger occurs after 30 patients enrolled (20 at the 0.25 mg/kg dose and 10 placebo control) then the first cohort 15 patients will be enrolled at the 0.50 mg/kg dose with randomization of 2:1 (treatment:placebo control). If no safety trigger occurs, the last cohort of 15 patients will be enrolled (10 at the 0.50 mg/kg dose and 5 placebo control).
- All SAE's will be reviewed by the DSMC/CEC every 15 patients enrolled and each death will be reviewed within 72 hrs of reporting. Safety trigger is defined as a greater than two patient differential in the occurrence of symptomatic intracranial hemorrhage or major acute bleeding event (defined below) within 72 hours between control and treatment arms.
- Randomization will be stratified according to site.

Tenecteplase and placebo will be provided by Genentech. They will be labeled accordingly indicating which vials contain active drug and which contain placebo. The DCC research pharmacy will de-identify the drugs for distribution to each study center (with tracking of all product) and therefore will remain unblinded to treatment randomization and will be in charge of assigning the correct vials for dosing. Study staff, investigators, and subjects will remain blinded to treatment assignments.

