6. STATISTICAL CONSIDERATIONS

6.1 DETERMINATION OF SAMPLE SIZE

Assuming a total of 60 subjects enrolled with a 2:1 ratio in the tenecteplase:control arms and a good outcome rate of 15% in the control arm, this study has approximately 70% power to detect an absolute difference of 35% in the good outcome rate between the combined tenecteplase arms (40 patients) and the control arm (20 patients) and approximately 55% power to detect an absolute difference of 35% between each of the tenecteplase arms (20 patients) and the control arm (20 patients), at the 2-sided 0.05 significance level based on the Fisher's exact test. Good outcome rate is defined as the proportion of patients who are alive and free of respiratory failure at 28 days. If the true rate of symptomatic ICH or major bleeding requiring transfusion is 3%, the chance of observing at least one of these events in 20 patients is at least 45%. The chance of observing at least one event in 20 patients increases to at least 70% if the true event rate is 6%.

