6.5 METHOD OF ANALYSIS

Continuous and categorical variables will be presented and summarized by using means with standard deviations and frequencies with percentages respectively. Tukey's method for pairwise comparison and large sample based multiple comparison of logits will be performed for continuous variables. Logistic regression modeling will be used for covariates adjustments and subgroup analyses. Survival functions will be estimated by applying Kaplan-Meier method. Statistical testing will be performed at two-sided 5% level of significance.

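### Randomisation is stratified by site, but no analysis of the primary outcome uses site: the one named test is an unstratified Fisher test, and Section 6.5 gives the outcome no test, effect estimate or confidence interval

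*Combined protocol and SAP*

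**What the plan says.** **Allocation.** Sections 3.1 and 4.2 describe 2:1 allocation in blocks of 15, two blocks per dose, at up to 6 centres. Section 4.2 adds: "Randomization will be stratified according to site". Note a of Appendix 1 gives the block as 10:5.

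**Test.** Section 6.1 takes "a good outcome rate of 15% in the control arm" and claims "approximately 70% power to detect an absolute difference of 35% in the good outcome rate" for pooled tenecteplase (40) against control (20), and about 55% for each dose (20 v 20), "at the 2-sided 0.05 significance level based on the Fisher's exact test". Fisher's test appears nowhere else.

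**Analysis.** Section 6.5 gives percentages for categorical variables, attaches its comparison of logits to continuous variables, and offers logistic regression for adjustment and subgroups without listing a covariate. It ends: "Statistical testing will be performed at two-sided 5% level of significance". Site is not mentioned.

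**Aim.** Section 3.3 says the study is not powered for significance and is "designed to provide an estimate of the potential benefit-signal".

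**The concern.** The trial builds site into the randomisation and then leaves it out of the analysis. When arms are balanced within sites and sites differ in prognosis, the treatment difference carries little between-site noise. An unstratified test still counts that noise in its error term, so it rejects too rarely under the null and gives up some power.

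There is also a reporting gap. A trial meant to estimate a benefit signal for phase III should specify an effect measure with an interval, and Section 6.5 has neither for the primary outcome. With no named test and no listed covariates, the primary analysis could be chosen after the data are seen.

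**Working it through.** **1. The plan's own figure.** Inputs from Section 6.1: 15% control, 15 + 35 = 50% active, two-sided 0.05, Fisher. Power is the sum, over all outcome pairs with Fisher p ≤ 0.05, of Bin(x; n₁, 0.50) × Bin(y; n₀, 0.15).
- 40 v 20: 74.5% (71.4% if the one-sided p is doubled); stated, about 70%.
- 20 v 20: 57.3%; stated, about 55%.

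The stated figures are rounded and slightly low, which is harmless.

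**2. Size with no site variation.** The same enumeration (40 v 20) with equal rates gives 3.4% at 15% and 3.5% at 20%. Fisher is therefore below 5% before site enters.

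**3. The stratified test.** For site k with n₁ₖ active, n₀ₖ control, Nₖ total, xₖ active successes and tₖ total successes:
- Eₖ = n₁ₖtₖ/Nₖ
- Vₖ = n₁ₖn₀ₖtₖ(Nₖ − tₖ)/[Nₖ²(Nₖ − 1)]
- CMH = [Σ(xₖ − Eₖ)]²/ΣVₖ, compared with χ² on 1 df, no continuity correction.

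**4. Simulation.** Assumptions not in the documents: six sites of 10; site effects Normal(0, SD) on the logit scale; balance within site (four sites 7:3, two sites 6:4, total 40:20). Overall rates were held at 15% and 50%, because Section 6.1 states overall rates. There were 40,000 runs per cell (6,000 for the exact stratified test); simulation error is about 0.2 points (0.6 for the exact test).

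| Site SD | Fisher | Chi-square | CMH | Exact stratified | CMH − Fisher |
|---|---|---|---|---|---|
| 0 | 74.7% | 80.7% | 78.8% | 73.9% | 4.1 |
| 0.5 | 74.7% | 81.0% | 80.5% | 77.3% | 5.8 |
| 0.75 | 74.9% | 81.2% | 82.2% | 78.4% | 7.3 |
| 1.0 | 75.0% | 81.3% | 84.1% | 79.9% | 9.1 |

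At SD 1.0, sites one SD either side of the middle have control rates of about 5% and 26%.

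**5. Splitting the gain.** At SD 0 site cannot matter, so the 4.1 points there come from comparing a discrete exact test with an asymptotic one. The remainder is 5.8 − 4.1 = 1.7, 7.3 − 4.1 = 3.2 and 9.1 − 4.1 = 5.0 points. Exact stratified against Fisher gives −0.8, 2.6, 3.5 and 4.9. With four sites of 15 and evenly spaced site effects, the like-for-like gain is about 1, 3 and 6 points at SD 0, 0.5 and 1.0. The site component is thus about 0 to 6 points.

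**6. Size with site variation.** At SD 1 and 20% in both arms, two separate simulations give Fisher 2.4% and 2.7%, and CMH 4.5% and 4.9%.

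**7. Blocks run across sites.** Each cohort is to hold exactly 10:5 over up to 6 sites. Separate blocks of 15 at every site would not guarantee that, so within-site balance is uncertain. With 40:20 fixed only trial-wide and six sites of 10, CMH against Fisher is:
- SD 0: 75.6 − 74.5 = 1.1 points
- SD 0.5: 77.6 − 74.8 = 2.8
- SD 0.75: 79.0 − 74.3 = 4.7
- SD 1.0: 81.3 − 74.4 = 6.9

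Fisher's size then stays at about 3.3 to 3.5%, so ignoring site adds no conservatism. The gain depends on the layout: four sites of 15 gave about 3 to 10 points over SD 0 to 1.0.

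**The case against.** **Fisher is not fixed as the analysis.** It appears only in the power calculation, and the logistic regression in Section 6.5 could include site. This stands. A reader might infer that the plan commits to an unstratified primary test, but the documents do not say so. The supported statement is that no test is assigned and site has no stated role.

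**Planned power is not reduced.** A reader might infer that power drops below the Section 6.1 figure once sites differ. A simulation that fixes 15% and 50% at an average site does show Fisher falling to about 61% at SD 1. In that set-up, however, the overall control rate rises to 18.8% and the difference shrinks to 50 − 18.8 = 31.2 points. With overall rates as Section 6.1 states them, Fisher stays near 75%.

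**The gain is mostly not about site.** Largely true. Against an unstratified chi-square test, balanced CMH gains −1.9, −0.5, 1.0 and 2.8 points in the table above. A single headline such as 10 or 11 points would be neither a bound nor a site effect: it mixes discreteness with an assumed SD, and the documents give no between-site variation.

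**Stakes are limited.** The error is conservative and Section 3.3 disclaims power. That lowers the urgency, but an estimation aim strengthens the case for a stated effect measure and interval.

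**Conclusion.** The point holds in a modest form. Site is a stratification factor with no stated place in the analysis, and Section 6.5 gives the binary primary outcome no test, estimate or interval. If allocation is balanced within sites, moving from unstratified Fisher to site-stratified CMH raises power from about 75% to 79–84% over assumed logit SDs of 0 to 1.0. About 4 points of that are discreteness and about 0 to 6 are site. If blocks run across sites, the total gain is about 1 to 7 points with six sites of 10. CMH was not below Fisher in any scenario run, and its size did not exceed 5% beyond simulation error at these SDs. All of this rests on assumed site numbers, sizes and spread. It is an efficiency and pre-specification gap, not a threat to validity or a loss of the stated power.

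**What to change.** In Section 6.5, state:

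> The primary comparison (pooled tenecteplase v placebo, all randomised patients) uses a Cochran-Mantel-Haenszel test stratified by site, with sites of fewer than 3 patients merged, and is reported as a Mantel-Haenszel risk difference with 95% CI. A version stratified by dose stage is a sensitivity analysis.

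The risk difference is Σ[(xₖn₀ₖ − yₖn₁ₖ)/Nₖ] / Σ[n₁ₖn₀ₖ/Nₖ], where yₖ is the number of control successes.

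Do not cross site with dose stage. That makes about 12 strata of 5 (60/12), and in simulation it lost power when neither factor mattered (69% v 73% for Fisher).

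In Section 4.2, state how the blocks of 15 combine with the site strata. If an amendment changes the stratification factor, analyse by the new factor.

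The cost is wording only, settled before unblinding. The downside is small: a site with only one arm has Vₖ = 0 and contributes nothing to the test.
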